11.1 Data confidentiality

Computer-based files will only be made available to personnel involved in the study through the use of access privileges and passwords. Wherever feasible, identifiers will be removed from study-related information. Lab staff may be privy to participant identity in that they will see participants pick up test kits but have been trained to maintain confidentiality. Precautions are in place to ensure the data are secure by using passwords and encryption, because the research involves web-based surveys.

11.2 Subject confidentiality

Research data will be obtained from participant surveys and interviews. All participants will provide informed consent prior to study participation. Research data that is obtained will be used for research purposes only. Patient identifiers will be used only for linkage purposes or to contact patients. The study identification number, and no other identifying information, will be used on all data collection instruments. All study staff will be reminded to appreciate the confidential nature of the data collected and contained in these databases. The Penn Medicine Academic Computing Services (PMACS) will be the hub for the hardware and database infrastructure that will support the project and is where the REDCap portal is based. The PMACS is a joint effort of the University of Pennsylvania's Abramson Cancer Center, the Cardiovascular Institute, the Department of Pathology, and the Leonard Davis Institute. The PMACS provides a secure computing environment for a large volume of highly sensitive data, including clinical, genetic, socioeconomic, and financial information. Among the IT projects currently managed by PMACS are: (1) the capture and organization of complex, longitudinal clinical data via web and clinical applications portals from cancer patients enrolled in clinical trials; (2) the integration of genetic array databases and clinical data obtained from patients with cardiovascular disease; (3) computational biology and cytometry database management and analyses; (4) economic and health policy research using Medicare claims from over 40 million Medicare beneficiaries. PMACS requires all users of data or applications on PMACS servers to complete a PMACS-hosted cybersecurity awareness course annually, which stresses federal data security policies

under data use agreements with the university. The curriculum includes Health Insurance Portability and Accountability Act (HIPAA) training and covers secure data transfer, passwords, computer security habits and knowledge of what constitutes misuse or inappropriate use of the server. We will implement multiple, redundant protective measures to guarantee the privacy and security of the participant data. All investigators and research staff with direct access to the identifiable data will be required to undergo annual responsible conduct of research, cybersecurity, and HIPAA certification in accordance with University of Pennsylvania regulations.

Data will be stored, managed, and analyzed on a secure, encrypted server maintained by Penn Medicine Nudge Unit and/or the Penn Center for Mental Health. All study personnel that will use this data are listed on the IRB application and have completed training in HIPAA standards and the CITI human subjects research. Data access will be password protected. Whenever possible, data will be de-identified for analysis.

11.3 Subject privacy

Interested participants will be directed to the REDCap platform where they will be asked to enter data related to eligibility. Participants can choose when and where to access this platform, maintaining their own privacy. There is the possibility that a participant's involvement in the study may be made known to other participants, as other study participants may be visiting the central lab location at the same time to pick up saliva sample collection kits. Other study participants will not have access to any personal information or other information collected throughout this study. All efforts will be made by study staff to ensure subject privacy.

11.4 Data disclosure

The following entities, besides the members of the research team, may receive protected health information (PHI) for this research study. The Office of Human Research Protections at the University of Pennsylvania -Federal and state agencies (for example, the Department of Health and Human Services, the National Institutes of Health, and/or the Office for Human Research Protections), or other domestic or foreign government bodies if required by law and/or necessary for oversight purposes.

11.5 Data safety and monitoring

The Principal Investigators and research team will closely monitor the safety, privacy, and data integrity of the study. Patients will be provided contact information for study staff and if adverse events are identified, events will be reported and brought to the PI's attention.

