8.2 Procedures

Once participants provide consent in REDCap, they will be directed to a page that provides an instructional video on what to do next. Participants will be instructed to take a saliva collection test kit. When they are ready to self-collect their saliva sample, they will be instructed to not eat or drink for 30 minutes prior to collecting their saliva and to collect saliva in an isolated room. Participants will then be instructed on how to inactivate the virus and bring their sample to their laboratory's central PCR machine, where they will take an assay test. They will be instructed to collect saliva into a 1.5mL collection tube containing inactivation buffer (TCEP and EDTA) using a small funnel and inactivate at 95°C for 10 minutes. Participants will then transfer 6ul of saliva into 2 PCR tubes containing amplification master mix and primers, put tubes in a heat block or PCR machine at 65°C for 45 minutes and assess fluorescence using a simple battery-powered fluorescence viewer. Once they assess their sample, they will be instructed to dispose of the saliva sample safely and in accordance with best laboratory practices. No saliva samples will be collected by the research team at any time as part of this study.

Each time a participant self-collects a saliva sample and runs the assay test, they will have the opportunity to pick up another saliva collection test kit. Each time they take another saliva collection test kit, they will scan a QR code (labeled for returning users) which will direct them to a simple REDCap prompting them for their name. We will use this data to record how many saliva collection kits are taken by each participant. Participants will be told they can do this point of care testing as frequently as they want (but no more than once a day for up to four weeks).

Each week for up to four weeks, consented participants will also be emailed a link to the online REDCap survey. Based on the week of their participation, they will be asked a battery of survey measures (see below list of surveys along with survey frequency table).

COVID SAFE 2.0 SURVEY MEASURES

Measures	Pre-consent	After training video and completing first test*	Week 1	Week 2	Week 3	Week 4
Screening Questions	X					
Use & POC testing		X	X	X	X	X
AIM, IAM, & FIM		X		X**		X**
Intervention Usability Scale (IUS)		X				X
User Burden Scale (UBS)		X				X
Participant Experience & Program Ease		X		X		X
Program Continuation & Availability		X				X
Demographics		X				

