*depending on what day of week participants consent to participate, these surveys will be collected at the Week 1 timepoint.

**At Weeks 2 and 4, we will use a single item adapted version of AIM, IAM, FIM

Survey Measures

- Questions about participant's use and results of test
 - o Note, results of test are self report. No saliva samples will be collected as part of this study. If participants self-report a positive result, they will be asked to self-report if they confirmed the positive result (i.e. by getting a CLIAA-approved test). Note, the confirmatory results are also self-report. No data will be entered into the EMR as part of this study.
- The 4-item Acceptability of Intervention Measure (AIM); the 4-item Intervention Appropriateness Measure (IAM); and the 4-item Feasibility of Intervention Measure (FIM; Weiner et al., 2017). We will also use a modified 1-item version of each of these measures. See table of survey measures.
- The Intervention Usability Scale (IUS)
- The User Burden Scale (UBS)
- Questions about the participant's experience with point of care testing and program ease
- Questions about program continuation and availability of testing to family members
- Demographics questions

During the pilot phase, we will check in with participants once to get real time feedback on changes to our test distribution method and rapidly adjust our workflow to refine our distribution method. During the second phase, we will scale up the program and make study enrollment available to all Penn faculty, trainees, and staff who work in person at a PSOM laboratory.

Participants will be instructed to follow standard university and department specific guidelines for isolation and return to work if the assay is positive.

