11.6 Risk/benefit

11.6.1 Potential study risks

All data described previously will be protected as described in the Subject confidentiality section. There is minimal risk to subjects as there is minimal risk of breach of data. Our team has extensive experience working with these types of data. We will use commercial-grade encryption to protect participant information. Their personal information will only be used by study team members who have been trained to use secure protocols to maintain the privacy of data. Risks and side effects related to this study include the possibility that answering certain questions on the surveys about symptoms may make study participants feel slightly uncomfortable or may be inconvenient. The risks of self-collecting a saliva sample for testing may include the possibility for false positives or false negatives, testing may induce feelings of fear or anxiety, a positive test result may cause participants to miss days of work, and individuals may experience mild discomfort if they receive the CLIA approved test. We expect the risks of picking up and dropping of test kits to be no more than the risk of returning to campus.

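### No systematic solicitation of adverse events is described, so a report of none could not be read as a low rate; the existing weekly survey could ask.

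*Combined protocol and SAP*

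**What the plan says.** Section 11.5 is the whole safety plan. It opens with a general commitment: "The Principal Investigators and research team will closely monitor the safety, privacy, and data integrity of the study". It then gives the one mechanism it describes: participants receive staff contact details, and "if adverse events are identified, events will be reported and brought to the PI's attention". It contains no definition of an adverse event, solicited question, time window or denominator.

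Section 8.2 sets up regular contact with all participants: "Each week for up to four weeks, consented participants will also be emailed a link to the online REDCap survey". The measures table and list there cover screening, use and test results, the AIM, IAM and FIM, usability, user burden, experience and program ease, continuation and availability, and demographics. The nearest items to harms are "Questions about the participant's experience with point of care testing and program ease" and the follow-up to a positive: "If participants self-report a positive result, they will be asked to self-report if they confirmed the positive result".

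Section 11.6.1 names foreseeable harms. They include false results, discomfort from the confirmatory test, and that "testing may induce feelings of fear or anxiety, a positive test result may cause participants to miss days of work". It also refers to survey questions about symptoms, which the measures list in 8.2 does not show.

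Section 9 describes the implementation outcomes and self-reported test results, relates outcomes by regression, and analyses interviews. It lists no harms. The single pilot check-in in 8.2 concerns how kits are distributed.

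**The concern.** Participants collect their own saliva, inactivate it by heat, "bring their sample to their laboratory's central PCR machine, where they will take an assay test", and pipette and read the reaction themselves. Events in that sequence, and the anxiety and lost work that the protocol expects, have no listed item that asks about them. Whether the team hears of them depends, as far as the text goes, on someone making contact.

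Two things are at stake. First, feasibility and acceptability are primary outcomes (section 3.1), and a favourable result for up to 500 testers is easily taken to imply that testing went without trouble. A count of spontaneous reports, with no known reporting probability and no denominator, could not support that. Second, the study moves from four pilot laboratories to all interested laboratories, and nothing in sections 5.1 or 8.2 calls for a look at problems during testing in between.

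**Working it through.** The plan states no event rate, error level or sample-size calculation, so there is no figure of its own to reproduce. The check has two parts.

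**Part 1: does each harm foreseen in 11.6.1 have a listed collection route in 8.2?**

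- False positive: yes, in part. Positive results and their confirmation are asked.
- False negative: no listed item.
- Fear or anxiety: no listed item; experience or user-burden questions might touch it, but their wording is not in the documents.
- Missed work after a positive: no listed item.
- Discomfort from the confirmatory test: no listed item.
- Spill, exposure or injury during testing: not named in 11.6.1, and no listed item. Section 5.5 does require knowledge of safe practice in a biological safety cabinet, so handling is recognised as an issue.

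**Part 2: what could a count of zero mean?**

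Inputs: n = 50 and n = 500, the enrolment ceilings in section 5.4. The probability s that an affected participant's event reaches the team is an assumption; the documents give no value, so a range is shown.

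With zero events reported, the one-sided 95% upper bound on the probability of a *reported* event is 1 − 0.05^(1/n). The reported probability is the true risk times s, so the bound on the true risk is [1 − 0.05^(1/n)] / s.

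- n = 500, s = 1: 1 − 0.05^(1/500) = 0.00597, or 0.60%.
- n = 50, s = 1: 1 − 0.05^(1/50) = 0.0582, or 5.8%.

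| Assumed s | Bound, n = 500 | Bound, n = 50 |
|---|---|---|
| 1 | 0.60% | 5.8% |
| 0.5 | 1.2% | 11.6% |
| 0.25 | 2.4% | 23.3% |
| 0.10 | 6.0% | 58% |
| 0.01 | 59.7% | no bound below 100% |

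Conversely, suppose the true risk were 2% with n = 500 (an illustrative value). The chance of no report at all is (1 − 0.02s)^500:

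- s = 1: 0.98^500, below 0.1%.
- s = 0.5: 0.99^500 = 0.7%.
- s = 0.10: 0.998^500 = 37%.
- s = 0.01: 0.9998^500 = 90%.

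The same silence is thus strong evidence or almost none, depending on a quantity that the plan neither states nor measures. Asking every participant does not make s equal to 1, but it gives a known number of respondents and a yes or no from each.

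**The case against.** The strongest reply is that this is a minimal-risk implementation study with no harm endpoint, run by people used to laboratory work. Section 8.2 has saliva collected in an isolated room into inactivation buffer and then heated to inactivate the virus; participants watch a training video and must know safe cabinet practice. Feasibility is measured by a perception scale, and no safety claim or go/no-go rule is planned. All of this is correct. It argues for a light method and keeps the point modest, but it is no reason not to ask when a weekly survey already exists.

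A reader might also infer more than the documents support:

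- *That harms are captured only if a participant contacts staff.* Section 11.5 does not make contact the exclusive route, and it also commits the team to monitoring safety. Contact is the only route described.
- *That no harm is captured.* Positives and their confirmation are asked, 11.6.1 says symptoms are asked about, and the experience items, burden items and interviews may pick up some problems.
- *That the survey reaches everyone.* The emailed link does; responses may not.
- *That zero reports carry no information.* They become uninformative only as s approaches 0. At s = 0.5 and a 2% risk, silence would be unlikely (0.7%).

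**Conclusion.** The point holds as a gap in collection and reporting. The protocol describes no systematic solicitation of adverse events, lists no survey item for them although it foresees anxiety and missed work, and plans no harms table. A statement that none occurred would be hard to interpret and could not be read as a low rate.

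The attainable bounds of about 0.6% (n = 500) and 5.8% (n = 50) assume enrolment to the ceilings, full response and full disclosure. If only half responded, they would be 1 − 0.05^(1/250) = 1.2% and 1 − 0.05^(1/25) = 11.3%. The values of s are assumptions used to show a range. The primary implementation outcomes are not affected. This is a cheap improvement to safety detection before roll-out, not evidence that participants are being harmed.

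**What to change.** 1. **Survey.** In the use-and-testing block of section 8.2, which is scheduled every week, add one yes/no item with a description field: any spill, exposure, injury, marked anxiety or other problem while collecting or running the test. After a self-reported positive, ask the number of workdays missed.
2. **Alert.** Send the study team an automatic REDCap alert on any yes, and name this route in section 11.5.
3. **Analysis.** In section 9, report the number and proportion of respondents with at least one event, with an exact interval, the number of respondents as denominator, and the number of surveys answered. Summarise workdays missed among those reporting a positive. One person may test up to daily for four weeks, so any per-run rate must allow for clustering within person; an exact binomial interval that treats runs as independent would usually be too narrow.
4. **Pilot.** Tabulate the pilot responses before phase two opens.
5. **Consistency.** Reconcile the symptom questions mentioned in 11.6.1 with the measures list in 8.2.

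The cost is two short items, one alert and one table. The downside is a slightly longer survey and some follow-up of alerts, including trivial ones.

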11.6 Risk/benefit

11.6.1 Potential study risks

All data described previously will be protected as described in the Subject confidentiality section. There is minimal risk to subjects as there is minimal risk of breach of data. Our team has extensive experience working with these types of data. We will use commercial-grade encryption to protect participant information. Their personal information will only be used by study team members who have been trained to use secure protocols to maintain the privacy of data. Risks and side effects related to this study include the possibility that answering certain questions on the surveys about symptoms may make study participants feel slightly uncomfortable or may be inconvenient. The risks of self-collecting a saliva sample for testing may include the possibility for false positives or false negatives, testing may induce feelings of fear or anxiety, a positive test result may cause participants to miss days of work, and individuals may experience mild discomfort if they receive the CLIA approved test. We expect the risks of picking up and dropping of test kits to be no more than the risk of returning to campus.

11.6.2 Potential study benefits

This unique program could improve the health of individuals by picking up on changes in symptoms earlier allowing individuals with COVID-19 to be identified quickly and reduce the spread of the virus. However, participants may receive no benefit from the study.

